This 5-year study evaluates the effects of a 10-week group-based linguistically translated and culturally adapted cognitive-behavioral stress and self-management (C-CBSM) intervention on symptom burden and health related quality of life (HRQoL) in Hispanic men treated for localized prostate cancer (PC). About 80% PC cases are diagnosed as early disease and have a 5- and 10-year survival rate of almost 100% and 99%, respectively. 1 Most patients receive active treatment (~70%) leading to prolonged treatment-related side effects and dysfunction persisting well beyond primary treatment.², ³, ⁴ Survival is offset by chronic side effects such as sexual and urinary dysfunction, pain and fatigue that can lead to poor psychosocial functioning, impaired intimacy and social functioning, and masculinity concerns. ^{5, 6, 7} Hispanic PC survivors report lower physical and social functioning, poorer emotional well-being and greater sexual and urinary dysfunction, even after accounting for SES and disease severity. These sequelae can lead to elevated glucocorticoid release and inflammatory cytokines that have a direct effect on these symptoms and can interfere with physiological pathways necessary for recovery of sexual and urinary functioning. We have shown that CBSM reduces symptom burden and improves HROoL in bilingual Hispanic PC survivors. In a pilot we showed that a linguistic translation of CBSM with attention to sociocultural processes improved symptom burden and HRQoL in Spanish monolingual PC survivors. We have also shown that CBSM is associated with reduced glucocorticoid resistance and inflammatory gene expression pathways in circulating leukocytes among breast cancer survivors. We propose to (a) deliver a culturally adapted C-CBSM intervention in Spanish that places greater emphasis on salient sociocultural determinants of symptom burden and HRQoL in Hispanics (e.g., fatalistic attitudes, family interdependence, perceived discrimination, machismo), (b) incorporate a neuroimmune model of symptom regulation and management, and (c) test the efficacy of C-CBSM, relative to standard non-culturally adapted CBSM, in two diverse Hispanic communities (Chicago & Miami). We will test our aims in 200 Hispanic men post-treatment for localized PC with elevated symptom burden in a 2 x 4 randomized design with condition (C-CSBM vs. CBSM) as the between groups factors, and time (baseline, postintervention & 6- and 12-months post intervention) as the within groups factor.

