Our **Primary Aim** is to determine whether randomization to C-CBSM, relative to standard CBSM, is associated with reduced symptom burden and improved HRQoL. Our **Secondary Aims** evaluate whether C-CBSM leads to greater improvements in the intervention targets (e.g., stress management, psychological distress & interpersonal disruption), and physiologic adaptation (i.e., glucocorticoid receptor sensitivity & inflammatory gene expression). We will also evaluate psychosocial and physiological mechanisms as mediators of C-CBSM's effects on our primary outcomes. We also **explore** several moderators (e.g., SES, acculturation, treatment, Hispanic origin) of C-CBSM's effect on primary outcomes and the effects of C-CBSM on cardiometabolic health (e.g., lipids, fasting glucose) via reduced inflammation.

Primary Aim:

Aim 1: Determine whether participation in C-CBSM is associated with significantly greater reductions in symptom burden and improvements in HRQoL relative to participation in CBSM.

Secondary Aims:

Aim 2: Determine whether participation in C-CBSM is associated with significantly greater improvements in intervention targets (i.e., improved stress management, and reduced psychological distress and interpersonal disruption) relative to participation in the CBSM condition.

Exploratory Aims:

- **Aim 3:** Explore whether participation in C-CBSM is associated with significantly greater activation of leukocyte glucocorticoid receptor and less inflammatory gene expression profiles relative to CBSM.
- **Aim 4:** Explore whether C-CBSM related improvements in symptom burden and HRQoL are mediated by improvements in intervention targets and gene expression profiles.
- **Aim 5:** Explore moderators of C-CBSM (e.g., SES, treatment type, acculturation, Hispanic ancestry) and C-CBSM's effects on cardiometabolic markers via reduced inflammation.

Integrated Model of Culturally Adapted Cognitive Behavioral Stress Management (C-CBSM) in PC: Our aims are guided by several theoretical frameworks. 8,9,10,11,12,13,14,15,16,17 Our approach is based on three predominant models: (a) psychosocial interventions impact clinically relevant outcomes (e.g., symptoms & HRQoL); (b) effects of psychosocial interventions on clinical outcomes are mediated by improvement in

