CBSM & Physiological Adaptation. We documented CBSM's effects on diurnal cortisol, circulating inflammatory markers and pro-inflammatory gene expression in circulating leukocytes. 124 In 84 PC survivors about 10.3 months post surgical or radiation treatment undergoing hormonal therapy, pro- inflammatory cytokines were associated greater symptom burden. Better urinary function pre- to post- CBSM was associated with decreases in both IL-1 (r=-.55) and IL-6 (r=-.40). Similarly, decreases in fatigue across the intervention period were associated with decreases in IL-1 \square (r=.41) and IL-6 (r=.35). We also found that decreases in IL-6 were associated with increases in both physical (r=-.38) and social (r=-.37) functioning, and decreases in anxiety (r=.40), while decreases in IL-1 were associated with decreases in both CES-D depression (r=.40) and an ABS negative mood composite (r=.41; all p's <.05). In stage 0-III breast cancer (BC) survivors, CBSM reduced cortisol, changed circulating numbers of specific leukocyte subsets and cytokine production by T lymphocytes. 121,123,124,125 CBSM-treated BC survivors also showed reductions in expression of leukocyte pro-inflammatory gene pathways and enhanced expression of innate antiviral gene pathways. Genome-wide transcriptional profiling and bioinformatics analyses were conducted at baseline and 6- and 12-months post-CBSM in 79 BC survivors randomized to CBSM or health promotion. At baseline, negative affect was associated with a >50% differential expression of 201 leukocyte transcripts. This included upregulated expression of pro-inflammatory and metastasisrelated genes. CBSM altered leukocyte expression of 91 genes by >50% at follow-up. Effects included downregulation of pro-inflammatory (e.g., IL-1A, IL6, TNFA) and metastasis-related (MMP9) genes and upregulation of Type I interferon (IFN) response genes. Promoter-based bioinformatic analyses showed a decreased activity of NF-kappaB/Rel and GATA family transcription factors and increased activity of IFN response factors and the glucocorticoid receptor, suggesting these as mediators of CBSM-induced reversal of upregulated inflammatory gene expression. 124 Although highly efficacious, active treatment (e.g., surgery & radiation; $\sim 70\%$ of cases) for localized prostate cancer (PC) can lead to significant symptom burden (i.e., sexual & urinary dysfunction) and compromises in multiple facets of health related quality of life (HRQoL). Hispanic PC survivors are at a physical and psychosocial disadvantage, yet evidence based treatments (EBTs) such as cognitive behavioral stress management (CBSM) that have proven effective in reducing symptom burden and improving HRQoL in cancer survivors have rarely targeted Hispanics or delivered culturally adapted CBSM in Spanish to diverse Hispanics in the context of a randomized behavioral clinical trial with an adequate sample size and long-term followup. This study will fill several critical gaps in our knowledge on the incremental efficacy of culturally adapted EBTs, relative to standard linguistic translations, on improving symptom burden and HRQoL in Hispanic men with localized PC, and map sociocultural, psychosocial and molecular mechanisms involved in the efficacy of CBSM, and therefore help guide targeted treatments for this critically understudied population and other Spanish speaking cancer survivors.

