We conduct genome-wide transcriptional profiling of monocytes, the cells that initiate and maintain most inflammatory responses. 160,161 For in-person blood collection 10-ml of blood are drawn into BD Cell-Separator Tubes. After PBMCs have been isolated through centrifugation, they are labeled with immunomagnetic beads against CD14, ¹⁶² a surface marker specific to monocytes. By passing the labeled cell suspensions through Mitenyi's autoMACS instrument, we can acquire a relatively pure (~90%) population of monocytes through positive selection. The acquired cells will then be lysed and stabilized (RNeasy Mini-Kits), 163 and frozen at -80°C until shipment to UCLA for transcriptome profiling assay. Again, both [name] and [name]'s lab have successfully implemented this protocol in previous collaborations with [name]. 157 [name] lab at UCLA will extract total RNA using PCR-clean and RNAse-free techniques, and check sample quantity and quality with NanoDrop 1000 and Agilent Bioanalyzer 2100 instruments. 150ng of the RNA will be transformed to fluorescent cRNA, hybridized to Illumina Human HT-12 bead arrays, and scanned on a Illumina iScan reader. Raw expression values will be quantile-normalized and log-2 transformed for statistical analysis, and the pool of differentially expressed genes will be identified by Linear Mixed Models that compare CBSM and C-CBSM groups, net of demographic and biobehavioral confounders (e.g. age, BMI, co-morbidities and disease-relevant confounders such as time of treatment, time since treatment). Differentially expressed genes are defined as those showing ≥1.5-fold difference between groups and a transcript-level false discovery rate of < 5% (using standard Benjamini & Hochberg stepdown analysis. 164 Up to 10 differentially expressed genes will be re-verified using quantitative RT-PCR with TaqMan gene expression assays (Applied Biosystems Inc.), a one-step enzyme system, 165 and manufacturer's specified thermal cycling protocol on a iCycler real-time PCR instrument (BioRad Inc.). To identify transcription control pathways underlying differential gene expression, we use a 2-sample variant of the Transcription Element Listening System (TELiS). 166 TELiS quantifies the prevalence of transcription factor-binding motifs within promoters of differentially expressed genes. Analyses focus on 3 transcription factors (TFs) by which C-CBSM could affect monocyte inflammatory activity: NF□B, the major pro- inflammatory TF; CREB, a TF that conveys adrenergic signals to monocytes, and whose activity reflects the amount of SNS signal reaching these cells' genome; and glucocorticoid receptor, a TF that propagates cortisol's anti-inflammatory signals within monocytes and, like CREB, indexes how much hormone signal these cells are registering. For the remote blood collection that is collected via dried blood samples (DBS) we will use standard DBS collection procedures that have been well validated and used by our research team (i.e., [name]). 200, 201 Briefly, the samples are collected by pricking the tip of the middle digit with a sterile disposable lancet, and then allowing drops of blood to wick onto filter paper cards Total RNA will be extracted from DBS samples by cutting 2-4 blood spots from the 5-spot filter paper for each sample (using a separate razor blade for each sample to prevent contamination), depositing all filter paper spots from each sample into 370 µL of RLT in an RNAse-free sterile 1.5 ml microcentrifuge tube, incubating the tube for 30 min at 37° C with agitation (1000 rpm), transferring tube contents (including filter paper) into a QIAshredder column for 60 sec microcentrifugation at maximum speed, after which the 360 µL of remaining RLT was processed through the QIAcube nucleic acid extraction system using RNeasy Micro Kit reagents, the manufacturer's standard operating protocol (including DNAse treatment), and a 20 µL elution volume. DBS samples are highly stable, can sit overnight at room temperature and can be mailed for subsequent storage in a -80 freezer. Samples will be stored/batched at [name] lab and mailed to Co-I [name]'s lab at Northwestern

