Hypothesis 2 (Aim 2): C-CBSM will show significantly greater improvements in intervention targets (i.e., improved stress management, and reduced psychological distress and interpersonal disruption) from baseline (T1) to 3-, 6- and 12-month follow-ups (T2-T4) relative to CBSM.

Test of Study Hypotheses. All analyses will be intent-to-treat analyses ¹⁹⁸ and linear mixed models will be used to test Hypotheses 1-2. These models classify time of measurement as a categorical variable in order to give full flexibility to different mean time courses in the two randomized groups. Latent growth modeling (LGM)¹⁸⁵ with relevant covariates is used to test the three sub-hypotheses of Aim 4. Advances in LGM and structural equations modeling (SEM)¹⁸⁶ allow us to blend these methods to test complex models of change¹⁸⁷ as latent growth models. LGM allows for missing data, as well as irregularly spaced measurements across time, time-varying and invariant covariates, accommodation of individual-specific deviations from the mean time trend and estimation of population variance associated with individual effects. Analyses of the first 3 hypotheses inform the functional form of the LGM time course. Software to implement these analyses is available (e.g. Mplus). ^{188,189} The software permits the blending of continuous and categorical data, the specification of linear and nonlinear models of change, and the specification of longitudinal structural models. Adequate model fit will be established by several fit indicators (Comparative Fit Index [CFI] > .95, Root-Mean-Square Error of Approximation [RMSEA] ≤ .05, Standardized Root-Mean-Square Residual [SRMR] < .08). ¹⁹⁰

Exploratory Hypotheses:

Hypothesis 3 (Aim 3): C-CBSM will show significantly greater activation of leukocyte glucocorticoid receptor (i.e., greater sensitivity) and lower inflammatory gene expression (i.e., less activation) pathways from baseline (T1) to 3-, 6- and 12-month follow-ups (T2-T4) relative to CBSM.

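### Hypothesis 3 reads glucocorticoid-receptor activation as receptor sensitivity, but nothing the trial measures can separate sensitivity from hormone level

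*Combined protocol and SAP*

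**What the plan says.** Under Exploratory Hypotheses, Hypothesis 3 states that "C-CBSM will show significantly greater activation of leukocyte glucocorticoid receptor (i.e., greater sensitivity"). The introductory paragraph on the aims names the quantity of interest as "physiologic adaptation (i.e., glucocorticoid receptor sensitivity & inflammatory gene expression"). The Power Analyses text likewise calls the receptor outcome sensitivity and says that it showed effects similar to those for inflammatory genes. The numbered Aim 3 and Hypotheses 4b and 4c speak of activation only.

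The measurement is set out under Genomic Level. Differentially expressed genes are found with mixed models comparing the arms "net of demographic and biobehavioral confounders (e.g. age, BMI, co-morbidities and disease-relevant confounders", and then "TELiS quantifies the prevalence of transcription factor-binding motifs within promoters of differentially expressed genes". Three transcription factors are examined. The glucocorticoid receptor is one of them, and the plan says that it, "like CREB, indexes how much hormone signal these cells are registering".

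**The concern.** Sensitivity means response per unit of hormone. Registered signal is the response that results from whatever hormone was present. The plan gives one index both meanings: registered signal in the assay section, sensitivity in the hypothesis. Equating them is safe only if hormone level is known, held fixed, or equal between arms, and the plan provides for none of these.

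What is at stake is the conclusion drawn from Aim 3. A positive result would be reported as improved receptor sensitivity, or as reduced glucocorticoid resistance, when the data could equally reflect a difference in cortisol. A null or negative result would be just as uninformative about sensitivity. Hypothesis 4b uses receptor activation as an outcome and 4c uses it as a mediator. Their wording is already sound, but their interpretation could inherit the label from Hypothesis 3.

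**Working it through.** **1. The plan's own figure.** The only number attached to this outcome is in Power Analyses: 0.48 SD detectable with 80% power at a two-sided 1% level and 100 in the C-CBSM group at T4. Taking 100 per arm, as that section does:

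d = (z for 0.995 + z for 0.80) × √(2/100) = (2.576 + 0.842) × 0.1414 = 0.483.

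Power at exactly 0.48 SD is 79.3%. The figure reproduces, and nothing in this point disputes it. It says how large a shift could be detected, not what a shift would mean.

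**2. What the index contains.** Write the index as S = f(H, R), where H is the hormone reaching the cells and R is receptor sensitivity, with S increasing in both. This is an assumption about form, but it needs only that more hormone or more sensitive receptors give more registered signal. In the simplest case, log S = log H + log R, the arm difference is

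Δlog S = Δlog H + Δlog R.

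Only the left side is observed. If Δlog H is unknown, any value of Δlog S is compatible with a positive, zero or negative Δlog R.

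**3. Whether the plan supplies H, or R at a known H.** The sections that list measurements give:

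- Medical & Disease Characteristics: free testosterone is the only hormone assayed.
- Cardiometabolic Health: triglycerides, HDL-cholesterol, blood pressure, CRP and fasting glucose; CRP only for blood spots.
- Inflammation and Systemic Level: IL-1b, TNF-a, IL-6, IL-10 and CRP; a shorter list for blood spots.
- Cellular Level: cells are stimulated with nine toll-like-receptor ligands. No glucocorticoid is added, so no response at a known hormone concentration is obtained.
- Genomic Level: the named adjustment variables do not include cortisol.
- Blood collection: home blood spots are taken in the afternoon or evening, and no clock time is given for in-person draws. Time of day therefore does not fix hormone level either.
- Confidentiality and Data Management: PSA and A1c are added. Cortisol is not.

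H is therefore neither measured nor held constant, and R is not measured directly.

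**4. Whether H can be assumed unchanged.** The plan's background does not allow this. The opening summary says of treatment side effects: "These sequelae can lead to elevated glucocorticoid release and inflammatory cytokines". The section on CBSM and physiological adaptation reports that in breast-cancer survivors "CBSM reduced cortisol, changed circulating numbers of specific leukocyte subsets". The background section on inflammation and symptom burden adds that CBSM improved the daily regulation of cortisol in preliminary work. Hormone level is thus something the plan expects this type of intervention to affect.

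**5. Earlier results under two names.** The background describes the breast-cancer finding from promoter-based analysis as increased receptor activity. The power text, apparently drawing on the same earlier study, calls it sensitivity. Activity is the term that matches the method described.

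**The case against.** The strongest reply is that the quantity tested is already activation. Aim 3, 4b and 4c say so; the sensitivity wording sits in one parenthesis, one line of the aims and one sentence on power; and no model, test or sample would change. The aim is exploratory. Both arms receive ten weeks of CBSM, so cortisol may not differ between them. Part of the expression analysis is deferred to a cited report, and the list of adjustment variables is only illustrative. All of this is fair and limits the point to labelling and interpretation. It does not remove it: equal cortisol in the two arms would be an untested assumption, and an unlisted adjustment for cortisol would still need a cortisol measurement, which appears nowhere.

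A reader might go further and infer that the plan will give the wrong sign, with a successful intervention lowering cortisol, lowering the index and being reported as worse sensitivity. The documents do not support that. The plan has no rule that scores a lower index as poorer sensitivity. The only reported fall in cortisol is in breast-cancer survivors, and the same section also reports increased receptor activity after CBSM. The preliminary work cited in the background speaks of better regulation, not lower levels. No cortisol difference between C-CBSM and CBSM is given. Nor can a false-positive rate be attached: the motif method is described as a two-sample comparison of gene sets, with no score per man and no between-man standard deviation.

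**Conclusion.** Wrong as written, within an exploratory scope. The index supports a statement about glucocorticoid-receptor-mediated transcriptional activity. It does not support a statement about receptor sensitivity or glucocorticoid resistance, whichever way the arms differ. This rests on the plan's own description of what the index reflects, on the absence of any cortisol measurement or glucocorticoid challenge from the listed procedures, and on the assumption that registered signal rises with both hormone level and sensitivity. No numerical size can be given, because the documents contain no between-arm cortisol effect. The 0.48 SD figure and the primary and secondary hypotheses (1 and 2) are unaffected. Hypotheses 4b and 4c need no rewording, only the same limit on how they are interpreted.

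**What to change.** - In Hypothesis 3, delete the parenthesis that equates activation with sensitivity.
- In the introductory paragraph on the aims and in Power Analyses, replace receptor sensitivity with glucocorticoid-receptor-mediated transcriptional activity.
- Add one sentence to the analysis plan: no conclusion on receptor sensitivity or glucocorticoid resistance will be drawn from this index, whether the arm difference is positive, negative or null, and this also applies when Hypotheses 4b and 4c are interpreted.

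The change needs no new samples, assays or models, and the sample size stands. Its cost is a narrower mechanistic claim. Keeping the sensitivity claim would require added measurement, such as cortisol in the same sample or a glucocorticoid condition in the ex vivo assay; the wording change does not depend on that.
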